8.5 Statistical Analysis of Study Results

8.5.1 General Statistics. Descriptive statistics will be generated for a comprehensive set of study variables to determine measures of central tendency and dispersion, as well as to characterize the nature of their distributions and whether outliers existed in the data. Continuous values will be reported as mean \pm standard deviation and categorical values as frequencies and percentages.

8.5.2 Analysis of the Primary Endpoint. The comparison of change in body weight from baseline to 48 hours between the two treatment groups constituted the primary endpoint. Hypothesis testing on this between-group change was performed by

nonparametric methods using the Wilcoxon rank-sum test via SAS PROC NPAR1WAY; a two-sided significance level of .05 was applied. This analysis of change in body weight was compared between all tolvaptan treated patients and all placebo treated patients on an intention-to-treat basis. Within-group changes over time were analyzed via the nonparametric Wilcoxon signed-rank test using SAS PROC UNIVARIATE under a two-sided significance level of .05. The second analysis of the primary study endpoint, comparison of change in body weight between treatment groups at 48 hours **with stratification** for baseline copeptin, will be conducted in the same manner as the priority comparison.

8.5.3 Analysis of Secondary Endpoints.

A two-sided significance level of .05 will also be applied to statistical testing of secondary endpoints with no adjustment for multiple comparisons.

8.5.3.1 Changes in VAS Scale. Changes in the VAS dyspnea scale will be analyzed via point estimates and corresponding standard deviations. Supportive between-treatment group comparisons will be conducted via the Wilcoxon rank-sum test.

8.5.3.2 Change in Loop Dose. For this continuous variable (dose of loop diuretic in furosemide mg equivalents) between-group comparisons will be assessed via t-test.

8.5.3.3 Loop Diuretic Adjustment. The Fisher's exact test will be used to assess between-group comparisons for this dichotomous variable.

8.5.3.4 Change in Loop Diuretic Score. For this ordinal variable between-group comparisons will be assessed via t-test.

8.5.3.5 Change in body weight from Visit 1 to Visit 3. This endpoint will be analyzed in a similar fashion as the change in body weight from Visit 1 to Visit 2.

8.5.4 Analysis of Exploratory Endpoints.

8.5.4.1 Change in Body Weight with Baseline Copeptin by Randomized Study Arm. This endpoint will be evaluated using Spearman Correlation analysis. The correlation coefficient between copeptin concentration at baseline and the change in body weight from baseline to 48 hours in the study patients within each of the two randomized arms (tolvaptan or placebo) will be determined. The two-sided 95% confidence interval will also be constructed. The Spearman correlation approach will be used as it is rank-based and does not make distributional assumptions.

8.5.4.2. Other Exploratory Endpoints. Planned between-group comparisons of continuous variables (copeptin, serum creatinine, and serum sodium) will be assessed via the Wilcoxon rank-sum test or t-test as appropriate.

9. Sample Size and Rationale

9.1 Sample Size.

The study will have a sample size of 40 patients, equally allocated to the two study treatment groups.

9.2 Power Calculation. The study power calculation was based on the primary analysis of the primary endpoint: change in body weight from baseline to 48 hours between the randomized study groups. Using experience in the preceding pilot study (8), a sample size of 40 patients will have 79% power to detect a difference of 1 kilogram in change in body weight between the study treatment groups (augmented loop diuretic + tolvaptan versus augmented loop diuretic alone) at the two-sided .05 significance level.

10. Safety and Adverse Events

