**Tolvaptan Treatment to Reverse Worsening Outpatient Heart Failure:
Possible Role of Copeptin in Identifying Responders
(TROUPER)**

NCT number NCT02476409
Document Date 03/07/2022

Study Protocol

Tolvaptan Treatment to Reverse Worsening Outpatient Heart Failure: Possible Role of Copeptin In Identifying Responders (TROUPER)

[name], MD
Principal Investigator

Co-Investigators, [name], BA, [name], ANP, ACNP, [name] on
behalf of the UNITE-HF investigative team at UNC-CH and the UNITE-HF Site Network

University of North Carolina at Chapel Hill

Version: 12.1

Version Date: 3-7-2022

1. Protocol Synopsis

Title:	Tolvaptan Treatment to Reverse Worsening Outpatient Heart Failure: Possible Role of Copeptin In Identifying Responders
Indication:	Heart Failure
Location:	Approximately 4-6 clinical centers in U.S.
Rationale:	Patients with worsening heart failure presenting in the outpatient setting represent a unique opportunity for novel approaches to decongestion that may more rapidly improve fluid status and symptoms as well as reduce the risk of hospitalization. In these patients with less severe congestion, combining the vasopressin antagonist tolvaptan with loop diuretic may represent a more effective strategy for decongestion. In addition, profiling copeptin may help identify patients in this unique population who are more likely to respond to tolvaptan.
Hypothesis:	This study is designed to test two related hypotheses 1) that the addition of oral tolvaptan to loop diuretic therapy will produce better decongestion than augmentation of loop diuretic therapy in patients presenting with worsening heart failure in the outpatient setting 2) that prespecified post hoc stratification on baseline copeptin level will be a predictor of the degree of superiority of oral tolvaptan plus loop diuretic compared to augmentation of loop diuretic.

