5.2 Randomization

All patients will be randomized using a block design to ensure roughly equal distributions of patients into each arm of the trial. Randomization will be stratified by clinical site.

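### Randomisation is stratified by site but no analysis uses site; a site-aligned rank test for 48-hour weight change would cost little and gain power if sites differ

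*Combined protocol and SAP*

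**What the plan says.** Section 5.2 states: "All patients will be randomized using a block design", and then: "Randomization will be stratified by clinical site". Section 5.3 repeats that the blocks are by site. The synopsis plans "Approximately 4-6 clinical centers in U.S".

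Section 8.5.2 gives the primary test as the "Wilcoxon rank-sum test via SAS PROC NPAR1WAY; a two-sided significance level of .05 was applied", with weight change "compared between all tolvaptan treated patients and all placebo treated patients on an intention-to-treat basis". The copeptin-stratified second analysis is to be run in the same manner, and section 8.5.3.5 treats weight change to Day 8 similarly. Copeptin is the only stratification factor in any analysis. Site appears in no primary, secondary or exploratory analysis.

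Sections 9.1 and 9.2 give 40 patients, "equally allocated to the two study treatment groups", and say that "a sample size of 40 patients will have 79% power to detect a difference of 1 kilogram in change in body weight" "at the two-sided .05 significance level". Site is not mentioned there.

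**The concern.** Stratified blocks keep the arms close to balanced within each site, so differences between sites cannot systematically favour one arm. A pooled rank test does not use that balance. It counts site differences as random noise, so its reference distribution is wider than the design warrants. The true type I error then falls below 5% and power is lower than it could be.

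The protocol itself leaves room for site differences. Preserved and reduced ejection fraction are both eligible (section 4.1), so case mix can vary. Section 5.5.1 leaves extra diuretic and changes to the augmented dose to the investigator. With 40 patients and a stated power of 79%, a few points matter.

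**Working it through.** **Inputs from the documents.** Difference 1 kg, 20 per arm, two-sided 0.05 (sections 9.1 and 9.2). Section 9.2 states no SD. The pilot's overall SD of weight change is 1.1 kg (section 2, Table 1; 24 hours after a single dose).

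**Assumed, because the documents do not say.** Five sites of 16/10/7/4/3 (total 40), blocks of 4, normal outcomes, additive site effects, no missing weights, and the between-site SD.

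**Step 1: the plan's own figure.** Standard error = 1.1 × √(2/20) = 0.348 kg, and 1/0.348 = 2.875. Normal approximation: Φ(2.875 − 1.960) = Φ(0.915) = 82.0%. The noncentral t gives 80.0%, and with the Wilcoxon efficiency 3/π it gives 78.1%. The stated 79% therefore reproduces with SD 1.1 kg. It does not with SD 1.0 (86.9% by t) or 1.2 (72.8% by t).

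**Step 2: tests compared by simulation.**
- Plain: the Wilcoxon rank-sum test on all 40 patients.
- Aligned: subtract the site mean from each weight change, rank the results across all patients, and test with the within-site permutation variance.

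**Step 3: total SD fixed at 1.1 kg, a share f of the variance between sites.** Site SD = 1.1√f and residual SD = 1.1√(1 − f). At f = 20% these are 0.49 and 0.98 kg.

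| Site share of variance | Plain | Aligned |
|---|---|---|
| 0% | about 77% | about 76% |
| 10% | about 79% | about 81% |
| 20% | about 81% | about 86% |

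**Step 4: site variance added to a residual SD of 1.1 kg.** Total SD = √(1.1² + site SD²).

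| Site SD (kg) | Total SD (kg) | Site share | Plain | Aligned |
|---|---|---|---|---|
| 0.3 | √1.30 = 1.14 | 0.09/1.30 = 7% | about 76% | about 77% |
| 0.55 | √1.5125 = 1.23 | 0.3025/1.5125 = 20% | about 71% | about 77% |
| 1.1 | √2.42 = 1.56 | 1.21/2.42 = 50% | about 56% | about 78% |

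**Step 5: type I error.** Over five other layouts of 4 to 6 sites, the plain test falls from about 5% to 3.4–4.6% at an added site SD of 0.5 kg and to 1.6–2.9% at 1.0 kg. With total SD fixed and a 20% share, it is 3.1–3.6% in the two layouts run. The aligned test stays near 5% throughout.

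**Step 6: cost when sites are alike.** Over those five layouts the aligned test loses 0 to 1.7 points. With one dominant site (30/4/3/2/1) power is 77.6 vs 74.8%, a loss of 2.8 points. With heavy-tailed residuals (t, 4 df) the loss is 1.4 to 2.8 points.

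**Step 7: the form of the test matters.** Van Elteren's test, the usual stratified Wilcoxon, costs about 3 to 6.5 points when sites are alike. Under PROC FREQ, SCORES=MODRIDIT re-ranks within site and becomes van Elteren (72.7% in the 16/10/7/4/3 layout). SCORES=RANK also re-ranks within site and gives 66.4%.

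**The case against.** The planned test is valid: its type I error does not exceed 5%, so a significant result stands. That is correct. A reader might infer from the mismatch between design and analysis that the primary p-value is unsound, and the documents do not support that.

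The large losses depend on adding site variance to 1.1 kg, which is the pilot's overall SD and the value that reproduces the stated 79%. With total SD held there, the plain test never falls below its power without site effects. The aligned test then offers an extra gain; nothing in the planned power is lost. This also stands. A reader might take the 56% figure as the trial's likely power. It needs half of all variance to lie between sites, which nothing in the documents suggests. The documents do not say how many sites the pilot used, so both readings of the SD are shown.

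The mechanisms are limited. A constant scale offset at a site cancels in a within-patient change, so differing scales are not an argument. Initial augmentation follows a formula (section 5.4), and dose changes made at Visit 2 come mostly too late to affect 48-hour weight. Case mix and unscheduled diuretic changes remain.

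The choice among valid tests is partly preference. ANCOVA with site reached 79 to 80% in the added-variance simulations. The aligned rank test has the merit of keeping the plan's nonparametric approach.

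**Conclusion.** The point holds as a cheap gain in efficiency. It does not show an error of validity, nor that the trial is underpowered. Site defines the randomisation strata and is absent from every analysis. On the assumed layout, aligning by site gains about 2 points of power at a 10% site share of variance and 4 to 5 at 20%, with total SD 1.1 kg. If site variance comes on top of a 1.1 kg residual SD, the gain is about 1 point at a site SD of 0.3 kg and 6 at 0.55 kg. At a variance share of 5% or less it is negligible. Against this stands a loss of about 0 to 2 points if sites do not differ, and about 3 in unfavourable cases such as one dominant site. Every gain depends on a between-site SD that the documents do not give.

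**What to change.** Make the change before unblinding. Section 2 records that the analysis plan was revised while blinded, so there is a route. If the data are already unblinded, leave the plain Wilcoxon as primary and label the aligned test as added afterwards.

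- **Section 8.5.2:** subtract the site mean from each 48-hour weight change and rank the aligned values across all patients. Test treatment with a CMH statistic stratified by site that uses those ranks directly as scores (PROC FREQ with SCORES=TABLE, not MODRIDIT or RANK).
- **Sparse sites:** state that a site with one patient, or with patients in only one arm, contributes no information to this test.
- **Section 8.5.3.5:** use the same method for weight change to Day 8.
- **Copeptin-stratified analysis:** it inherits the method of 8.5.2, and site-by-copeptin cells will be smaller still, so say whether alignment applies there.
- **Supportive analysis:** keep the plain Wilcoxon.

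The cost is a paragraph of SAP text and a few lines of code, plus the small loss of power given above if sites turn out alike. No new data are needed.

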5.4 Treatment Arms

Patients will be randomized in a 1:1 fashion to one of two types of treatment:

- Augmentation of current dose of loop diuretic + 30 mg of oral tolvaptan daily
 - Or
 - Augmentation of current dose of loop diuretic + placebo for tolvaptan

Doses of loop diuretics will be standardized to mg equivalents of furosemide based on 40 mg of furosemide for each 1 mg of bumex and 2 mg of furosemide for each 1 mg of torsemide. Augmentation of current dose of loop diuretic will be defined as doubling the current dose of oral loop diuretic if the total daily dose of loop diuretic is \leq 120 mg furosemide equivalents. If the total current oral dose of loop diuretic is $>$ 120 mg then the augmented dose of will be 50% of the current oral dose of loop diuretic + the current oral dose of loop diuretic in furosemide mg equivalents.

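### The 48-hour and Day 8 weight comparisons are valid but unadjusted, and forgo precision that baseline values already collected might supply

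*Combined protocol and SAP*

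**What the plan says.** Section 8.5.2 tests change in body weight from baseline to 48 hours by "nonparametric methods using the Wilcoxon rank-sum test via SAS PROC NPAR1WAY; a two-sided significance level of .05 was applied". The comparison is of whole arms: "This analysis of change in body weight was compared between all tolvaptan treated patients and all placebo treated patients on an intention-to-treat basis". It contains no covariate and no site term, and no adjusted sensitivity analysis appears anywhere in section 8. The second primary analysis (8.2.2) repeats the test within low and high copeptin groups, which is a subgroup comparison and not an adjustment.

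For the Day 8 weight endpoint, 8.5.3.5 states: "This endpoint will be analyzed in a similar fashion as the change in body weight from Visit 1 to Visit 2".

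Section 6.2.2 and Appendix A record body weight and current cardiovascular medications at baseline. Section 5.4 makes the on-study loop dose in both arms depend on the home dose: "Augmentation of current dose of loop diuretic will be defined as doubling the current dose of oral loop diuretic if the total daily dose" is at or below 120 mg furosemide equivalents, with a 50% increase above that. Section 5.2 stratifies randomization by site only.

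Section 9.2 states that "a sample size of 40 patients will have 79% power to detect a difference of 1 kilogram in change in body weight" "at the two-sided .05 significance level", and 9.1 splits the 40 patients equally between arms. The SD behind the 79% is not stated; 9.2 refers to the pilot study.

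**The concern.** Patients enter with different body weights and different home loop doses. Both are fixed before randomization, and both could plausibly affect how many kilograms a patient loses in either arm. Any variance they explain stays in the error term of an unadjusted test. This is the only comparison with a power calculation. It is planned at 79%, with no stated dropout allowance and no imputation (8.1.2).

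What is at stake is precision: some points of power, and the width of the interval around the treatment difference. Section 8.5.2 provides for neither an estimated difference in kg nor a confidence interval, so a covariate-adjusted estimate would also fill that gap.

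**Working it through.** **Inputs.** There are 20 patients per arm (9.1), a difference of 1 kg and two-sided 0.05 (9.2). The SD of weight change is 1.1 kg, from all 20 pilot patients in Table 1 of Background and Rationale. Total R² for the two covariates is not in the documents, so it is assumed over a range.

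**Reproducing the 79%.** The standard error of the difference is 1.1 × √(2/20) = 0.348 kg, so the noncentrality is 1/0.348 = 2.87.
- Two-sample t-test, 38 df: 80.0%.
- Rank-sum, with n scaled by its relative efficiency of 0.955 (19.1 per arm): 78.1%.
- Rank-sum by simulation with normal data: about 78%.

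The stated 79% is therefore the power of the unadjusted analysis.

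**Adding two baseline covariates.** The residual SD is 1.1 × √(1 − R²), with 36 df. The formula ignores chance covariate imbalance. The simulation (20,000 trials per row, random covariates sharing R² equally) includes it.

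| Total R² | Residual SD (kg) | ANCOVA, formula | Rank-sum, simulated | ANCOVA, simulated | Rank ANCOVA, simulated |
|---|---|---|---|---|---|
| 0 | 1.100 | 79.9% | 78.2% | 78.1% | 75.8% |
| 5% | 1.072 | 81.9% | 77.9% | 79.7% | 77.0% |
| 10% | 1.044 | 83.9% | 77.6% | 81.8% | 78.9% |
| 20% | 0.984 | 87.9% | 77.4% | 85.8% | 82.8% |

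A second set of 8,000 trials per setting gave 78.5%, 78.0% and 76.3% at R² 0 (rank-sum, ANCOVA, rank ANCOVA). It gave 78.0%, 81.9% and 79.6% at 10%, and 77.3%, 85.8% and 83.4% at 20%. Type I error was close to 5% for all three methods.

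**Change from rank-sum, both sets together.** ANCOVA changes power by about 0, +4 and +8 points at R² of 0, 10% and 20%. Two-covariate rank ANCOVA changes it by about −2, +2 and +6 points, and breaks even at roughly 6 to 10%.

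**Same result in patients and interval width.** The equivalent unadjusted sample size is 40/(1 − R²): 44 at 10% and 50 at 20%. Ignoring the lost degrees of freedom, interval width scales by √(1 − R²): √0.90 = 0.95 and √0.80 = 0.89.

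**What chance imbalance can do.** A covariate imbalance of one standard error shifts the estimated difference by √R² × 0.348 kg. That is 0.08 kg for a covariate explaining 5% of variance and 0.11 kg for one explaining 10%. Two standard errors double these to 0.16 and 0.22 kg, against a 1 kg target.

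**The case against.** The strongest reply is that nothing here is wrong. The rank-sum test is valid under randomization, is prespecified and matches the power statement. It also resists outliers. That stands, and it is why the point concerns efficiency only.

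A reader might infer that an imbalance in home diuretic dose could pass for a drug effect. With 20 per arm, imbalance is common: a given covariate differs between arms by more than 0.3 SD with probability about 34%. But chance imbalance is already covered by the 5% error rate, and the shifts computed above are small against 1 kg.

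A reader might also take Table 1 as evidence of a sizeable R². The pilot copeptin split accounts for (20 × 0.45²)/(20 × 0.45² + 18 × 1.0²) = 4.05/22.05 = 18% of weight-change variance. That figure does not carry over. It concerns a different variable, every pilot patient received tolvaptan, and patients were chosen from the copeptin extremes. It says nothing about body weight or home dose in both arms.

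Two objections to home dose as a covariate also stand. First, under 5.4 the added dose is not monotone in home dose: 120 mg adds 120, 160 mg adds 80 and 240 mg adds 120. If weight loss follows the increment, ranked home dose captures it imperfectly. With an assumed spread of doses, rank ANCOVA then gave 77.2% and 79.2% at R² of 5% and 10%, against about 77.6% for rank-sum. Second, the furosemide equivalent is not consistently defined. Section 5.4 equates 1 mg of torsemide with 2 mg of furosemide and 8.3.2 equates it with 20 mg. Ranks of torsemide users depend on which is applied.

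Finally, this is version 12.1, written after review of blinded aggregate data, and the primary endpoint was deliberately left unchanged. A late change to the test needs a clear record that it preceded unblinding.

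**Conclusion.** This is a cheap improvement, not a defect. The priority and Day 8 weight comparisons are sound as written, and the documents support neither a reading that they are biased nor one that the 79% is overstated for the planned test.

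What holds is that they leave unused two baseline values the trial already records. Using them is worth about +4 points (ANCOVA) or +2 (rank ANCOVA) at a total R² of 10%, and +8 or +6 at 20%. If neither covariate predicts weight loss, ANCOVA costs essentially nothing and two-covariate rank ANCOVA about 2 points.

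These figures assume normal data, an SD of 1.1 kg and an R² that the documents do not give. Baseline weight may predict kilograms lost only weakly. The SD comes from a 24-hour, single-dose pilot in stable patients. At 1.2 kg, t-test power would be about 73%, and precision would matter more.

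**What to change.** Before unblinding, amend 8.5.2 and carry the same wording into 8.5.3.5:

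- Prespecify an analysis of weight change adjusted for baseline body weight. Add home furosemide-equivalent loop dose as a second covariate only after the torsemide conversions in 5.4 and 8.3.2 have been reconciled. Use no further covariates at this sample size.
- Report the ANCOVA-adjusted difference in kg with its 95% confidence interval. If the sponsor wants to keep a rank-based test, use a rank ANCOVA: rank the change and the covariates, regress, and compare residuals between arms.
- Retain the unadjusted rank-sum result, and state which analysis decides the priority comparison. The power gain arises only if the adjusted analysis decides; otherwise the benefit is a kg estimate with an interval that may be narrower.

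If unblinding has already occurred, leave the rank-sum test as the priority analysis and present the adjusted one as supportive and post hoc.

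The cost is SAP wording, a few lines of SAS and the reconciliation of the conversion factor. The downside is up to about 2 points of power if rank ANCOVA is chosen and neither covariate predicts weight loss.

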In the current study design, assessment of the association of copeptin with the therapeutic response to tolvaptan will be done post hoc. Samples for analysis of copeptin will be obtained throughout the study but assays will not be performed until after the study is completed. The proposed principal analysis of the predictive role of copeptin for tolvaptan response will be based on post hoc stratification of the study population by baseline copeptin level. The current plan is to base this post hoc stratification on the results of a recently completed pilot study of the association of pre-treatment copeptin level with the effect of tolvaptan on change in body weight in patients with chronic stable heart failure due to reduced ejection fraction.

Results from this pilot study by our group provide preliminary data to suggest that copeptin may indeed be an effective way to identify patients with heart failure who have greater response to tolvaptan. A total of 20 outpatients with chronic stable symptomatic heart failure and history reduced left ventricular ejection fraction (≤ 40) were enrolled in the pilot study. Patients were selected for later enrollment by targeting those with upper or

lower quartile copeptin levels determined during an outpatient screening period (n=10 each). Patients received a single dose of 30 mg of tolvaptan and body weight, fluid intake and urine output were monitored in a clinical research unit for 24 hours. For analysis, patients were divided into two groups using a prespecified cut point based on their baseline copeptin level determined during their study hospitalization (≥ 10 versus < 10 pmol/L). Results comparing key study variables based on this prespecified cut point approach are shown in Table 1. These findings demonstrate that change in body weight, reflecting the net aquaretic response to tolvaptan, was greater in the subgroup of patients with baseline copeptin levels ≥ 10 pmol/L.

Table 1. Changes in body weight and fluid status after tolvaptan by baseline copeptin

Study Group	All Patients	Copeptin ≥ 10 pmol/L	Copeptin < 10 pmol/L	*P value
N	20	10	10	
Baseline Copeptin (pmol/L)	13.1 ± 9.7	20.5 ± 8.7	5.7 ± 1.9	<0.001
Change in Body Weight (Kg)	-0.8 ± 1.1	-1.3 ± 1.0	-0.4 ± 1.0	0.035
Net Output (mL)	1360 ± 1881	2091 ± 1662	630 ± 1876	0.089
Total Output (mL)	6141 ± 2072	6498 ± 2328	5784 ± 1835	0.853
Total Input (mL)	4780 ± 1664	4406 ± 1398	5154 ± 1893	0.393

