Hypotheses. This study is designed to test two related hypotheses 1) that the addition of oral tolvaptan to augmented loop diuretic therapy will produce better decongestion than augmentation of loop diuretic therapy alone in patients presenting with worsening heart failure in the outpatient setting and 2) that prespecified post hoc stratification based on baseline copeptin level will be a predictor of the degree of superiority of oral tolvaptan plus augmented loop diuretic compared to augmentation of loop diuretic alone.

Objectives. This study is designed to address the following objectives:

The objectives of this study will be to compare the effects of oral tolvaptan plus augmented loop diuretic versus augmented loop diuretic on 1) short term changes in body weight with and without stratification for baseline copeptin and 2) indices of congestion in patients presenting with worsening congestive heart failure in the outpatient setting with and without prespecified post hoc stratification based on baseline copeptin level.

4. Study Overview and Patient Cohort

This study will be a randomized, double blind, positive control, multi-center clinical trial enrolling patients who present in the outpatient setting with signs and symptoms consistent with worsening congestive heart failure. The sample size for the study is 40 patients. Candidates for the study will be identified by screening outpatients presenting with worsening heart failure. Patients who qualify and consent for the study will be enrolled within 24 hours of identification. Patients will be observed in a hospital setting following the initial administration of randomized therapy as outlined in detail below. Assuming they tolerate study treatment during this observation period, patients will leave the hospital setting and the remainder of the study will consist of observation during outpatient visits or telephone follow-up to assess response to randomized therapy. Patients will receive study medication through Day 8 of the study.

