8.2.2 Second Analysis of the Primary Endpoint

The second analysis of the primary study endpoint will be change in body weight between treatment groups at 48 hours with stratification for baseline copeptin. This approach will stratify study patients into subgroups based on their baseline copeptin level. Change in body weight will be compared between tolvaptan and placebo stratified according to baseline copeptin levels into low and high groups, in a similar manner to that described above for the primary analysis of the primary endpoint. A single prespecified cut point for baseline copeptin will define low and high copeptin in the randomized subgroups. Originally, this cut point was defined as < 10 pmol/L based on the previous pilot study of the relationship of baseline copeptin to tolvaptan response described in the background section of the protocol. However, recent studies in patients with volume overload, suggest that few patients in the current protocol would have values < 10 pmol/L. Therefore, the prespecified cut point will be determined based on blinded analysis of the baseline copeptin levels in the current study. This cut point will be determined taking into consideration the distribution of copeptin levels present in the study population at baseline. Additional cut points may be proposed based on the unrestricted correlation analysis of the changes in body

weight related to baseline copeptin in the randomized subgroups as described below (8.5.4.1). The copeptin guided hypothesis predicts that patients with elevated baseline copeptin who are treated with tolvaptan will have a significantly greater weight loss than placebo treated patients.

Table 2. Analysis of Treatment Effect by Baseline Copeptin

	Tolvaptan + Augmented current loop	Augmented current loop	Change in Body Weight
Baseline Copeptin Level	Low	Low	Weight change will be similar in 2 treatment groups
	High	High	Weight change will be > in Tolvaptan + Augmented current loop

8.3 Secondary Endpoints: Ordered by Clinical Importance.

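### Hypothesis 2 is about how tolvaptan's effect differs by copeptin level, but no planned analysis estimates that difference

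*Combined protocol and SAP*

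**What the plan says.** The Synopsis and section 3 state hypothesis 2 in nearly the same words. In the Synopsis, stratification by baseline copeptin "will be a predictor of the degree of superiority of oral tolvaptan plus loop diuretic compared to augmentation of loop diuretic".

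The pilot in section 2 motivates this. Weight loss after one tolvaptan dose "was greater in the subgroup of patients with baseline copeptin levels" of 10 pmol/L or more: -1.3 against -0.4 kg in Table 1. The pilot had no placebo arm.

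For the analysis, section 8.2.2 says: "Change in body weight will be compared between tolvaptan and placebo stratified according to baseline copeptin levels into low and high groups". Section 8.5.2 gives the method: the analysis stratified "for baseline copeptin, will be conducted in the same manner as the priority comparison", that is, the Wilcoxon rank-sum test at two-sided .05. Section 8.2.2 also states a prediction, that "patients with elevated baseline copeptin who are treated with tolvaptan will have a significantly greater weight loss than placebo treated patients". For the low-copeptin row, Table 2 expects: "Weight change will be similar in 2 treatment groups". The threshold is still open: "the prespecified cut point will be determined based on blinded analysis of the baseline copeptin levels in the current study".

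The only other analysis linking copeptin to weight response is section 8.5.4.1, a Spearman coefficient with a 95% confidence interval, computed separately in each arm. Section 9.2 sizes the trial for the unstratified comparison only.

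**The concern.** A degree of superiority is a tolvaptan-minus-placebo difference. To say copeptin predicts it is to say that this difference is larger at high copeptin than at low. The quantity needed is therefore a treatment-by-copeptin contrast, and no section defines one, gives it an interval or tests it.

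The planned outputs do not replace it:

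- **Separate rank-sum tests** give one p-value in each copeptin group. The prediction in 8.2.2 uses only the high-group p-value, which cannot depend on what happens at low copeptin. A non-significant result in a small low group does not show that weight change is similar there.
- **One stratum-adjusted test**, if that is what stratification means here, addresses the average effect across strata.
- **The two Spearman coefficients** are an informal look at effect modification, but they are not compared. The tolvaptan-arm coefficient alone cannot separate prediction of drug response from a general relation between copeptin and weight change.

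Copeptin as a marker of responders is in the trial's title, is one of its two hypotheses and forms the second component of the primary endpoint. As planned, the trial could report results that match 8.2.2 and Table 2 when copeptin has no bearing on the effect.

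**Working it through.** **Inputs.** 40 patients, 20 per arm; 1 kg difference; two-sided .05; stated power 79% (sections 8.5.2, 9.1, 9.2). Section 9.2 gives no SD. I assume 1.1 kg (all pilot patients, Table 1), with 1.0 kg (within copeptin groups, Table 1) and 1.5 kg (a stress case) as the range. Outcomes are taken as normal. The cut point is unset, so the high/low split per arm is assumed: 10/10, with 7/13, 13/7 and 15/5 as alternatives, the same in both arms.

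**The plan's own figure.** The t-test noncentrality is 1/(1.1 × √(1/20 + 1/20)) = 2.87 with 38 df, which gives 80.0% power. Simulating the rank-sum test gives 78.2%. Both agree with 79%, so SD 1.1 is consistent with the plan. SD 1.0 gives 86.9% and does not reproduce it.

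**Planned tests when copeptin does not matter.** The effect is 1 kg in both copeptin groups (simulated rank-sum tests, SD 1.1):

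| High/low per arm | High group significant | Low group not significant | High significant, low not |
|---|---|---|---|
| 7/13 | 28% | 44% | 12% |
| 10/10 | 44% | 56% | 25% |
| 13/7 | 55% | 71% | 39% |
| 15/5 | 63% | 83% | 52% |

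The groups are independent, so the last column is the product of the two before it; at 10/10, 0.444 × 0.563 = 0.25. At 10/10 the three figures are 52%, 49% and 25% for SD 1.0, and 26%, 74% and 19% for SD 1.5.

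**Planned tests when copeptin does matter** (10/10, SD 1.1). High significant and low not occurs in:

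- 42% of trials for effects of 1 against 0 kg
- 63% for 1.45 against 0.55 kg (average 1 kg, with the pilot's 0.9 kg gap)
- 92% for 2 against 0 kg

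The pattern carries some information, but it moves with group size as well as with effect modification. The high-group result alone is 44% for 1 against 0 kg, exactly as for 1 against 1 kg.

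**One stratum-adjusted rank test** (van Elteren, 10/10, SD 1.1) is significant in 77% of trials for a uniform 1 kg effect, 74% for 1.45 against 0.55 kg and 60% for 2 against 0 kg. It says almost nothing about hypothesis 2.

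**The direct contrast.** Contrast = (tolvaptan − placebo, high) − (tolvaptan − placebo, low).

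- SE = SD × √(sum of 1/n over the four cells) = 1.1 × √(4/10) = 0.70 kg.
- 95% half-width = 2.03 × 0.70 = 1.4 kg (36 df). It is 1.3 kg at SD 1.0 and 1.9 kg at SD 1.5.
- At 15/5: 2.03 × 1.1 × √(2/15 + 2/5) = 1.6 kg.
- If the split is 13/7 in one arm and 7/13 in the other (randomization is stratified by site only): 2.03 × 1.1 × √(2/7 + 2/13) = 1.5 kg.
- Under a uniform effect it rejects in about 5% of trials at every split, as it should.
- Power at 10/10, SD 1.1: 29% for 1 against 0 kg (34% at SD 1.0, 18% at SD 1.5), 24% for 1.45 against 0.55 kg, 80% for 2 against 0 kg.

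**The Spearman pair** (20 per arm, uniform effect). Significant on tolvaptan but not on placebo occurs in 2% of trials if copeptin is unrelated to weight change. It occurs in 14%, 23% and 24% if copeptin is related to weight change equally in both arms (assumed 0.3, 0.5 and 0.7 kg per SD of log copeptin). Comparing the two coefficients directly on the Fisher z scale rejects in 4% to 5% throughout; the half-width is 1.96 × √(2 × 1.06/17) = 0.69.

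**The case against.** The strongest reply is that section 8.2.2 says what the copeptin hypothesis predicts, a tolvaptan advantage in patients with elevated copeptin, and that the high-group test addresses exactly this. On that reading the 44% is subgroup power, not an error rate: with a uniform effect tolvaptan does work in the high group. That description of the 44% is right. But the narrower statement does not replace the hypothesis in the Synopsis and section 3. The figure is used here only to show that meeting the narrower prediction cannot separate a uniform effect from a modified one.

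Second, no section makes high significant, low not significant a decision rule; Table 2 only lists expectations. That also stands, but the plan offers no other criterion for judging hypothesis 2.

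Third, means and SDs under 8.5.1, if reported by arm and copeptin group, would let a reader work out the contrast. That is possible, but the plan commits neither to that breakdown nor to an interval, and 8.2.2 allows further cut points after the correlation analysis.

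Fourth, a single pooled stratum-adjusted test is the less likely reading of the plan. Agreed; the conclusion does not depend on it.

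Fifth, the contrast is weak at 40 patients, and a mean-scale form departs from the rank-based primary method. Both are true. Low precision is a reason to report an interval and not rely on two p-values. A rank-based or continuous contrast would also be defensible.

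**Conclusion.** The concern holds. Hypothesis 2 is a statement about effect modification, and nothing in sections 8.2.2, 8.5.2 or 8.5.4.1 estimates it. With a uniform 1 kg effect, the 8.2.2 prediction would be met in about 44% of trials (26% to 63% over the SDs and splits tried). The significance pattern suggested by Table 2 would appear in about 25% (12% to 52%).

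These figures assume normal outcomes, an SD taken from a 24-hour uncontrolled pilot in stable patients, and a copeptin split that is not yet known. The gap itself depends on none of these assumptions. It is worth fixing because copeptin is central to the trial's stated purpose. The powered unstratified comparison in 8.2.1 is unaffected.

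**What to change.** In 8.2.2 and 8.5.2, add the difference between the high- and low-copeptin treatment effects (each tolvaptan minus placebo in mean weight change at 48 hours), with a 95% confidence interval, at the single blinded cut point. Name it as the estimate on which hypothesis 2 is judged. Report each group's effect with its own interval, and state that a non-significant low group will not be read as similarity. Optionally, add an interval for the difference between the two Spearman coefficients in 8.5.4.1, as a rank-based sensitivity analysis that needs no cut point.

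The cost is one or two sentences in the analysis plan and no new data. A mean-scale estimate sits well with 8.5.1, which already reports means and SDs. The drawback is imprecision, so the plan should present the contrast as estimation and say that 40 patients may leave hypothesis 2 unresolved.
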